**3 TRIAL SCHEMA****Table 1: VACCINATION SCHEDULE**

The doses, methods and schedule of immunisation are described below.

PART I							PART II	
	Group	N	Month 0	Month 3	Month 6		N	Vaccinations 1,2,&3
ARM 1	A	6	Oral placebo	CN54gp140 +Oral placebo +I.M placebo	CN54gp140 +Oral placebo +I.M placebo		12	Selected dosage from Part I
	B	6	Ad4-EnvCN54	CN54gp140 +Oral placebo +I.M placebo	CN54gp140 +Oral placebo +I.M placebo			
	C	6	Ad4-EnvCN54	CN54gp140 Ad4-EnvCN54 +I.M placebo	CN54gp140 +Oral placebo +I.M placebo			
	D	6	Ad4-EnvCN54	CN54gp140 Ad4-EnvCN54 +I.M placebo	CN54gp140 Ad4-EnvCN54 +I.M placebo			
ARM 2	E	6	Oral placebo	CN54gp140 +MVA-CN54 +Oral placebo	CN54gp140 +MVA-CN54 +Oral placebo		max 12	
	F	6	Ad4-EnvCN54	CN54gp140 +MVA-CN54 +Oral placebo	CN54gp140 +MVA-CN54 +Oral placebo			
	G	6	Ad4-EnvCN54	CN54gp140 +MVA-CN54 +Ad4-EnvCN54	CN54gp140 +MVA-CN54 +Oral placebo			
	H	6	Ad4-EnvCN54	CN54gp140 +MVA-CN54 +Ad4-EnvCN54	CN54gp140 +MVA-CN54 + Ad4-EnvCN54			
		48					max 12	

## 4 TRIAL ASSESSMENT SCHEDULE

TABLE 2 - SCHEDULE OF VISITS, IMMUNISATIONS AND ASSESSMENTS - PART 1 & PART 2

Visit		1	2	3	4	5	6	7	8	9	10	11
Study Month		M0			M3			M6				M12
Study Week		W0	W1	W4	W12	W13	W16	W24	W25	W26	W28	W48
Study Day		D0	D7	D28	D84	D91	D112	D168	D175	D182	D196	D336
Visit Windows (Days)	-90		±1	±2	(1) -7/+14	±1	±2	(1) -7/+14	±1	±2	±2	±14
Immunizations		X			X			X				
Informed consent	X											
Medical history/ demographics	X											
General physical examination	X											
Entry screen for Ad4 neutralising antibodies	X											
Symptom directed physical exam		X	X	X	X	X	X	X	X	X	X	
Concomitant medications	X	X	X	X	X	X	X	X	X	X	X	
Vital signs	X	X 	X		X 	X		X 	X	X	X	
Inspection of administration sites (I.M)	X				X 	X		X 	X			
Solicited Adverse Events		X 	X		X 	X		X 	X			
Review Solicited AE on diary card			X			X			X			
Unsolicited Adverse events		X 	X	X	X 	X	X	X 	X	X	X	
Serious adverse events		X	X	X	X	X	X	X	X	X	X	X
Urine pregnancy test (women) 	X	X			X			X				X
Routine safety bloods 	X	X	X		X	X		X	X	X	X	
Antinuclear antibody and immunoglobulin  tests	X											
HIV test 	X	(X)	(X)	(X)	(X)	(X)	(X)	(X)	(X)	(X)	(X)	X
HBV, HCV and syphilis tests	X											
STI screen 	X											
Blood for serum – Immunogenicity		X		X	X		X	X	X	X	X	X
Blood for PBMC – Immunogenicity		X		X	X		X	X	X	X	X	X
Blood for PBMC – Infectivity		X		X			X		X	X	X	X
Mucosal antibody responses (rectal / genital / nasal)		X		X	X		X	X		X		X
Rectal swab for Ad4-EnvCN54 PCR		X	X	X		X	X		X	X	X	X
Rectal biopsies (optional; Part 2 only)		X 								X 		X 

 The second and third vaccinations (visits 4 and 7) can be shifted by -7 or up to +14 days. Subsequent visits would be shifted by the same number of days to ensure the interval to subsequent visits is maintained

 Confirmed negative prior to vaccination

 The parameters are detailed in section 12.3.3

 HIV testing at additional time points may be performed upon request of the volunteer and principal investigator or designee as medical or social circumstances warrant

 Genital swabs or urine for *Neisseria gonorrhoea* and *chlamydia trachomatis* will be collected

 Pre-dose, and at 60 (+/-10) min post-dose

 Immunoglobulins IgA, IgG and IgM

 Biopsy may be performed up to 2 weeks before vaccination

 Window for biopsy is -2 to +7 days

 Window for biopsy -56 to +56 days

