#### 12.2 VACCINATION AND FOLLOW-UP VISITS

- The assessments that will be performed at each visit are described in Table 2.
- Participants will be required to make 11 scheduled outpatient visits over the course of 48 weeks. Time 0 will start on the day of enrolment, which is also the day of randomisation and the first immunisation, and must be within 90 days after screening.
- Vaccinations will take place at Weeks 0 (Month 0), 12 (Month 3) and 24 (Month 6).
- Serum and peripheral blood mononuclear cells (PBMC) will be collected for immunogenicity at Weeks 0 (enrolment), 4, 12, 16, 24, 25, 26, 28 and 48.
- Adverse events will be assessed during the enrolment visit before and after immunisations and at every visit thereafter until the final safety visit at Week 28; thereafter only serious adverse events will be recorded.
- Injection sites will be inspected vaccination days at Weeks 12 and 24 (pre-dose and 60 (+/-10) min post-dose), and at Weeks 13 and 25.
- Symptom-directed physical examinations will be done at Week 0 and at every visit thereafter until the final safety visit at Week 28.
- Vital signs will be done on vaccination days (pre-dose and 60 (+/-10) min post-dose) and at Weeks 1, 13, 25, 26 and 28.
- Concomitant medications will be collected at every visit up to the final safety safety visit.
- Blood for routine laboratory safety parameters will be collected at Weeks 0 (enrolment), 1, 12, 13, 24, 25, 26 and 28 and at any other visit if clinically indicated.
- Mucosal samples for antibody responses (genital / rectal / nasal) will be collected at Weeks 0, 4, 12, 16, 24, 26 and 48.
- Urine pregnancy test will be assessed at Weeks 0, 12, 24 and 28.
- Rectal swabs for Ad4-EnvCN54 PCR will be assessed at Weeks 0, 1, 4, 13, 16, 25, 26, 28 and 48.

- Rectal biopsies will be assessed at Weeks 0, 26 and 48 for participants in **Part 2** of the clinical trial only. Participants may opt out of this procedure.

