### 12.2.2 VISIT WINDOWS

The second and third vaccination visits scheduled for weeks 12 and 24 will be compliant with the protocol if they take place -7 / +14 days either side of the target date determined by the date of the previous vaccination. If there is a delay >4 weeks a decision will be made by the TMG (see **section 20.1**) as to whether immunisation will continue.

The post-immunisation safety visits scheduled for weeks 1, 13 and 25 will be compliant with the protocol if they take place +/- 1 day of the target date determined by the date of the previous vaccination.

The primary endpoint visit (Visit 9; Week 26) and final safety visit scheduled for week 28 will be compliant with the protocol if they take place  $\pm$  2 days either side of the target date determined by the date of the third vaccination. The follow-up visit at Week 48 will be compliant with the protocol if it takes place  $\pm$ 14 days either side of the target date determined by the date of the third vaccination.

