### 12.4 PROCEDURES FOR ASSESSING IMMUNOGENICITY

Samples (indicated below) will be collected at the timepoints specified in Table 2 and transferred to the [name] Laboratory for analysis.

**Cervico-vaginal secretion samples** will be collected from female participants using a commercially available, self-inserted menstrual cup, at the time points indicated in Table 2, except at visits when female participants are menstruating in which case cervico-vaginal secretions will not be collected. In the case of light spotting, a sample **will** be collected.

**Rectal secretion samples** will be collected from male and female participants. Absorbent swabs will be held against the rectal wall for 2 minutes. Should a participant not wish to have a proctoscopy the swab may be inserted by the nurse or doctor or self-inserted by the participant, 3 cm into the anal canal.

**Semen samples** will be collected from male participants whilst within the clinical trials unit or brought into the clinic following donation at the time points indicated in Table 2. Semen samples should be donated following 24 hours of sexual abstinence, and produced  $\leq 2$  hours before being handed to clinic staff.

**Nasal secretion samples** will be collected from male and female participants using nasal synthetic absorptive matrix at the time points indicated in Table 2.

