### 14.2 OUTCOME MEASURES

#### 14.2.1 PRIMARY ENDPOINTS

##### *Immunogenicity*

Antigen specific mucosal (cervico-vaginal for women, semen for men, and rectal and nasal for all) antibody ( $\mu\text{g}/\text{ml}$ ) responses two weeks after the final immunisation.

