## 19 FINANCE

The clinical trial activities and acquisition of product, data management and analysis are funded by the Medical Research Council.

Participants will be reimbursed for their time, effort and for costs to cover their travel expenses to the study site and any inconvenience caused due to study participation. Participants will receive £150 per vaccination visit, £100 for screening / safety and follow-up visits up to a total of £1350 over the course of the study. Only enrolled participants will be paid for the screening visit.

Participants who undergo rectal biopsies in Part 2 will be paid an extra £50 per biopsy if it is done on the same day as other procedures/assessments scheduled at the same time-point, or an extra £100 if they have to make an additional visit to the site for the biopsy.

There are no bonuses or per participant incentives paid to staff.

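### In Part 2 the optional week-26 rectal biopsy may come before, or on the same day as, the primary-endpoint rectal secretion swab, so blood from the biopsy site could carry serum antibody into that sample

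*Protocol*

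**What the plan says.** **Endpoint.** Protocol section 14.2.1 defines the primary immunogenicity endpoint as "Antigen specific mucosal (cervico-vaginal for women, semen for men, and rectal and nasal for all) antibody" responses two weeks after the final immunisation. SAP section 10.1.1 keeps all of these sites and ranks nasal first.

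**Swab.** Protocol section 12.2 states: "Mucosal samples for antibody responses (genital / rectal / nasal) will be collected at Weeks 0, 4, 12, 16, 24, 26 and 48". Under section 12.4 the rectal sample is taken with an absorbent swab pressed to the rectal wall for 2 minutes. A participant who declines proctoscopy may instead have the swab inserted 3 cm into the anal canal.

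**Biopsy.** Table 2 in protocol section 4 has the row "Rectal biopsies (optional; Part 2 only") with an entry at Visit 9, week 26. Footnote 9, attached to that entry, reads "Window for biopsy is -2 to +7 days". It does not say which day the window is counted from. Section 12.4 has forceps biopsies taken from the left and/or right rectal wall at sites chosen by the doctor. Its only remark on healing concerns the interval from one biopsy to the next.

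**Visit window.** Section 12.2.2 lets Visit 9 fall "2 days either side of the target date determined by the date of the third vaccination".

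**Same day.** Section 19 sets one payment for a biopsy "if it is done on the same day as other procedures/assessments scheduled at the same time-point" and a higher one for a separate visit.

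**Analysis.** SAP section 12.2.1.2 pools 6 participants from Part 1 and 6 from Part 2 in each expanded group, 24 in all. Its mixed model has arm and gender as fixed terms and participant as a random effect.

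**The concern.** A swab of the rectal wall is meant to measure antibody in the secretion. If it follows a forceps biopsy of the same wall by hours or a few days, it may also pick up blood or exudate. Week 26 is two weeks after the last boost, when vaccine-specific serum antibody should be present, so any blood on the swab would be read as mucosal antibody.

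Three things could follow:

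- Rectal IgG and IgA could be inflated in biopsied participants.
- Part 1 and Part 2 participants in the same pooled group would have been sampled under different conditions, because only Part 2 participants can be biopsied. The model has no term for Part or biopsy to absorb this.
- If the arms differ in serum titre, leakage would pull the rectal contrast towards the serum contrast.

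The distinction matters in this trial. Protocol sections 2 and 7.6 expect group A to have no mucosal responders but detectable systemic responses, and one of the fallbacks in SAP section 3.2 would expand group A into Part 2.

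**Working it through.** The plan states no figure on this point, so there is none to reproduce. The check covers timing, exposure and an illustrative size.

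**1. Timing.** Let *b* be the biopsy day and *v* the swab day.

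- *Window counted from the actual visit.* Then *v* = 0 and *b* runs from −2 to +7, which is 10 allowed days. Two precede the swab (−2, −1), one is the same day (0) and seven follow it. So 3 of the 10 days allow a swab after the biopsy.
- *Window counted from the target date.* Then *b* runs from −2 to +7 and *v* from −2 to +2. The offset *b* − *v* has minimum −2 − 2 = −4 and maximum 7 − (−2) = +9. The biopsy can be up to 4 days before the swab or 9 days after it.

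**2. Is there a safeguard?** Protocol section 4 gives the window without an order. Section 12.4 describes both procedures but does not put the swab first, keep the two sites apart, or say what to do with a blood-stained rectal sample. Section 12.4 does have a blood rule for cervico-vaginal sampling, which is skipped during menstruation. The SAP has no rule for rectal samples taken after a biopsy.

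**3. Exposure.** Two expanded groups × 6 new participants = 12. The Part 2 analysis has 2 × 12 = 24, so at most 12/24 = 50% are exposed. Opt-outs and biopsies done after the swab reduce this.

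**4. Illustrative size.** The documents give neither a serum level nor a blood fraction, so both are assumed. With blood fraction *f*, plasma fraction 0.55 and specific serum IgG *C* in µg/ml:

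added ng/ml = *f* × 0.55 × *C* × 1000

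| Assumed *C* (µg/ml) | Added at *f* = 1% (ng/ml) |
|---|---|
| 1 | 0.01 × 0.55 × 1000 = 5.5 |
| 10 | 0.01 × 0.55 × 10,000 = 55 |
| 100 | 0.01 × 0.55 × 100,000 = 550 |

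If the contaminant is treated as serum rather than whole blood, the factor 0.55 drops out and 1% adds 10, 100 or 1000 ng/ml.

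**5. Effect on a pooled mean.** If *k* of the 12 participants in a group carry an added amount *d*, the group mean rises by *k* × *d* / 12. At the ceiling *k* = 6 this is *d*/2: 2.75, 27.5 or 275 ng/ml for the whole-blood figures above. The arm difference is biased by the difference between the two groups' shifts. That is zero if *k* and *d* are equal in both groups, and it follows the serum contrast if they are not.

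**The case against.** **The order may be set elsewhere.** Protocol section 16.2 mentions trial-specific procedure manuals, and the Laboratory Analysis Plan is not among the documents. Either could put the swab first on the day. This stands as a reason not to assume that same-day biopsies were done first. It does not remove the 2 early days that footnote 9 itself permits.

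**Contamination is inferred.** Nothing in the documents shows that a swab would carry blood, or how much. A longer gap allows more healing, so 4 days is not worse than 2. A swab inserted only 3 cm into the anal canal may not touch the biopsy site. All of this stands: the mechanism is plausible and its size is unknown.

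**Most allowed days are harmless.** Seven of the ten days follow the visit, section 19 only provides for a same-day biopsy without requiring it, and biopsies are optional. So 12 of 24 is a ceiling.

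**Rectal is not the leading site.** The SAP gives nasal secretions first place. That lowers the weight of the point, but rectal antibody remains in the primary endpoint and is tested separately.

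A reader might also infer more than the documents support:

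- *That group selection is compromised.* The 100 ng/mL rectal IgA pass criterion in SAP section 3.2 is applied to Part 1 participants, who are not biopsied. It is also an IgA threshold, so it is no yardstick for the IgG figures above.
- *That week 0 is affected in the same way.* Entry criteria exclude HIV infection and any earlier HIV-antigen vaccine (protocol section 9.2), so before vaccination there is no vaccine-induced antibody for blood to carry.
- *That the wide week-48 biopsy window is a primary-endpoint problem.* Week-48 durability is exploratory (section 14.2.3).
- *That light spotting in cervico-vaginal samples is part of this point.* That rule ("In the case of light spotting, a sample" is still taken) has nothing to do with biopsies and is the same in every group and both Parts.

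**Conclusion.** The point holds for week 26 in Part 2. The written window lets the biopsy precede a primary-endpoint rectal swab by up to 2 days, or up to 4 if counted from the target date, and same-day order is left open. This is more than a missing detail, because the early days are expressly allowed.

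At most 12 of 24 participants in the pooled Part 2 analysis are exposed, 6 per expanded group. Part 1 results and the choice of groups are untouched.

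The amount of carry-over cannot be estimated from the documents. The figures of 5.5, 55 and 550 ng/ml rest wholly on the assumed serum levels, 1% blood and a plasma fraction of 0.55. They show only that a small blood fraction could matter if serum titres are high. The documents do not support a claim that rectal results are in fact contaminated. They support closing an avoidable route to bias in one component of the primary endpoint, at little cost.

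**What to change.** **Protocol, Table 2 footnote 9.** Replace the window with: '0 to +7 days after the Visit 9 rectal secretion swab'. This also settles the reference day.

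**Protocol section 12.4.** Add: 'At week 26 the rectal secretion swab is collected before any biopsy.' Both changes are needed, because the narrower window alone would not settle the same-day order. The swab should stay at its visit and not be moved to an early biopsy date, so that it remains alongside the other week-26 samples.

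**SAP section 12.2.1.2.** Add a sensitivity analysis of the Part 2 week-26 rectal IgG and IgA results that excludes swabs taken after a biopsy or in unknown order. Report how many are excluded in each group.

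**If sampling is complete.** The SAP is dated July 2021 and describes the trial's conduct in the past tense, so the protocol changes may come too late. The sensitivity analysis can still be done from recorded biopsy and swab dates, with same-day pairs of unrecorded order counted as unknown.

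**Cost.** The biopsy window loses its 2 early days, and there is one extra analysis. No procedure is added for participants.

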## 6 ABBREVIATIONS

Ab	Antibody
ADCC	Antibody-dependent cell-mediated cytotoxicity
ARD	Acute respiratory disease
AE	Adverse event
ALP	Alkaline phosphatase
ALT	Alanine aminotransferase
AR	Adverse reaction
AST	Aspartate aminotransferase
BMI	Body Mass Index
CF	Consent form
CRF	Case Report Form
CTA	Clinical Trial Authorisation
CSR	Clinical Study Report
CTM	Clinical Trial Manager
EDC	Electronic Data Capture
ELISA	Enzyme Linked Immunosorbent Assay
ELISpot	Enzyme Linked Immunosorbent Spot Assay
ERC	Endpoint Review Committee
EUDRACT	European Union Drug Regulatory Agency Clinical Trial
GCP	Good Clinical Practice
HHC	Household Contact
HIV	Human immunodeficiency virus
IB	Investigator Brochure
ICF	Informed Consent Form
ICH	International Conference on Harmonisation
ICL	Imperial College London
ICS	Intracellular cytokine staining
ID	Intradermal
IDES	Internet Data Entry System
IDMC	Independent Data Management Committee
IM	Intramuscular
IMP	Investigational Medicinal Product

IRB	Institutional Review Board
ISF	Investigator Site File
ITT	Intention-to-treat
JRCO	Joint Research Compliance Office
LC	Langerhans Cell
mBC	Memory B cell
MHRA	Medicines and Healthcare Products Regulatory Agency
NHS	National Health Service
PBMC	Peripheral Blood Mononuclear Cell
PCR	Polymerase Chain Reaction
PIS	Participant Information Sheet
PI	Principal Investigator
POC	Proof of Concept
PP	Per-Protocol
QA	Quality Assurance
QC	Quality Control
R&D	Research and Development
REC	Research Ethics Committee
SAE	Serious Adverse Event
SAP	Statistical Analysis Plan
SAR	Serious Adverse Reaction
SOP	Standard Operating Procedure
SUSAR	Suspected Unexpected Serious Adverse Reaction
TMG	Trial Management Group
TOPS	The Overvolunteering Prevention System
UAR	Unexpected Adverse Reaction
UKHVC	UK HIV Vaccine Consortium

## 7 INTRODUCTION AND BACKGROUND

At the end of 2012, an estimated 35.3 million people were living with HIV worldwide, up 17% from 2001. This reflects the continued large number of new HIV infections and a significant expansion of access to antiretroviral therapy (ART), which has helped reduce AIDS-related deaths, especially in more recent years (UNAIDS Report on the global AIDS epidemic 2013. Geneva 2013). The majority of new HIV infections continue to occur in sub-Saharan Africa. There is an urgent need to strengthen and scale-up existing and new prevention methods such as HIV testing and counselling, behavioural interventions, condom use, treatment of sexually transmitted diseases, harm reduction, male circumcision (Wamai et al. 2011) and antiretroviral drugs for prevention (Granich et al. 2011). New prevention strategies to control the epidemic and prevent new infections, including pre-exposure prophylaxis (Kim et al. 2010), antiviral treatment for prevention (Granich et al. 2011), topical microbicides (Krakower et al. 2011), and HIV preventive vaccines must be explored and their access ensured. Although combination ART has transformed life expectancy, and global initiatives such as PEPFAR and the Global Fund to fight AIDS, TB and Malaria have made these drugs widely available, treatment has had limited impact on the number of new HIV infections. In the UK, even against a backdrop of comprehensive treatment and care services, sexual transmission of HIV continues unabated with an estimated incidence of 1-3 per 100 person years amongst young homosexual men. Whilst we hope that the strategic use of ART to prevent infection will increase, the need for an efficient and realistic vaccine regimen against HIV-1 remains a priority for global public health (Kim et al 2010; Rerks-Ngarm et al 2009; Koff 2010).

### 7.1 THE STATUS OF THE FIELD

Important findings from the Thai RV144 trial indicate that a vaccine regimen based on a non-replicating vector prime and a recombinant monomeric HIV envelope subunit protein (rgp120) boost could reduce the incidence of HIV-1 acquisition (Kim et al 2015).

The RV144 phase IIb clinical efficacy trial provided an important proof of concept that HIV acquisition can be reduced with a vaccine regimen based on a non-replicating pox vector prime, and an Envelope subunit protein boost. However, the observed level of efficacy (31%) is likely insufficient to provide a cost effective vaccine. Interestingly the reported efficacy of the RV144 vaccine at 12 months was 60%, but rapidly waned in conjunction with systemic antibody levels. Mucosal antibody levels, thought to be critical in preventing HIV acquisition and known to wane more rapidly than those in the systemic compartment, were not measured in the RV144 trial. Nevertheless it is widely accepted that a vaccine capable of delivering a sustained efficacy of  $\geq 60\%$  would be clinically useful in both developing (Andersson et al 2011) and developed world settings (Long et al 2011). However this is dependent on the level of coverage and the required frequency of boosting to maintain protective immunity. This trial has now become the benchmark for future studies. The products to be evaluated in this study (Ad4HIV phase I) offer significant potential to improve on this initial and important proof of concept. Specifically, we anticipate that the novel use of a mucosal replicating vector will maximize and maintain mucosal responses providing a durable efficacy of  $\geq 60\%$ , significantly lengthening the potential interval between required re-vaccination, a critical consideration for cost effectiveness.

The modest protective efficacy of the RV144 regime over 36 months (31%) highlights the need for both increased efficacy and durability of immune protection. In this respect live-

attenuated viral vaccines have been far more effective in preventing viral infections in humans and animal than any other approach, providing a compelling case for delivery of an HIV vaccine with a live vector (Parks et al. 2013). This is mirrored by results in the rhesus macaque model in which live-attenuated viruses like the nef deleted SIV-mac239 have proven to be the most effective experimental vaccine for preventing AIDS (Koff et al. 2006). However a live attenuated HIV vaccine is impractical based on significant inherent safety risks. Given that sexual transmission of HIV-1 is the predominant mode of HIV acquisition in adults, a key element for a successful preventative vaccine may be the ability to generate potent immune responses not only within the systemic circulation but also at the mucosal portals of entry (genital tract and rectum). Therefore a mucosal replication competent (live) virus vector may have additional advantages compared to non-replicating vaccines for priming mucosal and systemic responses.

